9.7 SARS-CoV-2 infection since randomization

With testing for anti-Nucleocapside IgG at visits 1 (baseline), visit 2 (=d14) and visit 5 (end of study) subjects will be assessed for SARS-CoV-2 infection since randomization. For all vaccination regimens the proportion of infections between d0, d14 and visit 5 (based on an anti-Nucleocapside IgG at visit 2 indicative of SARS-CoV-2 infection) will be compared descriptively reporting absolute numbers and percentages.

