4.4.2. Exclusion criteria

- Prior to study entry the subject got vaccinated with a regimen not included in the above list.
- Last anti-SARS-CoV-2 vaccine dose administered less than one month prior to study entry.
- Vaccination against a disease other than COVID-19 within 2 weeks prior to study entry. Only exception: Influenza vaccination which is allowed at any time.
- Subjects with any significant or uncontrolled disease posing a risk due to vaccination as judged by the investigator.
- Current immunosuppressive therapy, for example continuous glucocorticosteroid treatment equivalent to >10 mg/day prednisolone.
- Subject simultaneously participates in another clinical trials or has participated in the past 30 days.
- Subjects unable to report solicited adverse events.
- Subject participates or participated in Part A of this trial.
- Subject with any contraindications to the vaccines in the trial. A list of contraindications as listed in the Summary of medicinal Product Characteristics (SmPC, the Fachinformation in Germany), if appropriate.

- Use of drugs with significant interaction with the investigational product according to the SmPC or similar documents.
- Diseases or findings that may have a significant effect on the target variables and which may therefore mask or inhibit the therapeutic effect under investigation.
- Subject had COVID-19 or tested positive for SARS-CoV-2 within the last 3 months.
- Persons with any kind of dependency on the principal investigator or employed by the sponsor or principal investigator.
- Legally incapacitated persons.
- Persons held in an institution by legal or official order.

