9.3.1 Supportive analyses for the primary endpoint

In additional supportive analysis, the primary endpoint will be determined in the same way for each cohort separately, i.e., further supportive analyses will be performed based on different pre-vaccination series. Especially, within each cohort the multiplicity adjustment will be implemented as described above. The data will be visualised with bar charts.

To evaluate whether there is a difference between the two randomised intervention groups in the binary primary endpoint, a Cochrane-Mantel-Haenszel test will be applied stratified by the initial cohort vaccine strategy (cohort 4 to 9).

Furthermore, a logistic regression model will be performed using the primary endpoint as dependent variable. In the logistic regression models intervention group will be used as main factor. Based on the logistic regression model odds ratio (OR) and the corresponding 95% confidence intervals will be reported to evaluate whether there are differences between the two study intervention groups. In the logistics analyses we will also adjust for factors such as initial vaccination regimens (factor cohort), age and sex. We will also account for the different time lags between the 2nd and 3rd doses in further sensitivity analysis, e.g., including the number of days between vaccinations as additional covariate in the analysis models. Furthermore, descriptive tables will be provided stratified by taking into consideration the vaccination regimens.

In addition to the binary primary endpoint, the antibody titre values of visit 1 and 2 will be analysed on the metric scale (see analyses planned for secondary endpoints).

9.3.2 Impact of Covid infections between baseline and day 14

With testing for anti-Nucleocapside IgG at visits 1 (baseline), visit 2 (=d14) and visit 5 (end of study) subjects will be assessed for SARS-CoV-2 infection since randomization. Overall and for all vaccination regimens the proportion of infections between d0 and d14 (based on an anti-Nucleocapside IgG at visit 2 indicative of SARS-CoV-2 infection) will be compared descriptively.

In further logistic regression models the impact of having had a Covid infection between visit 1 and visit 2 on the primary endpoint will be explored by using it as additional factor.

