Additionally, a sensitivity analysis will be performed on the per protocol analysis set, including only subjects who have been vaccinated and not having had a new infection between visit 1 and visit 2 using the anti-Nucleocapside IgG measurements of visit 1 and 2.

For subjects where the exact timepoint of an externally confirmed infection is available (i.e. subjects reports date of a SARS-CoV-infection confirmed outside study procedures, captured by AE reporting), a further sensitivity analysis will be performed excluding only those patients who had a an externally confirmed infection between randomisation and the observation of the primary endpoint.

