9.4.3 Linear Models & Adjustment for Covariates and Mixed Models

When analysing the data from all study visits (e.g., Visit 1, Visit 2 and Visit 5 for immunogenicity data such as Anti-RBD or anti-N IgG), mixed model for repeated measurements (MMRMs) will be applied using subject ID as random factor using an unstructured covariance matrix. The last value before randomisation (baseline) will be used as covariate in the MMRM.

Similarly as described for the logistic regression models for the primary endpoint (see supportive analyses for the primary endpoint), also in the MMRs we adjust for factors/covariates such as initial vaccination regimens (factor cohort), age and sex. We will also address for the different time lags to previous vaccinations, e.g., for the time between the 2nd and 3rd doses and between the 3rd and 4th doses, respectively in further sensitivity analysis, e.g., including the number of days between vaccinations as additional covariate in the analysis models.

The impact of new covid infections after baseline on the secondary endpoints will be explored similarly to the primary endpoint analysis. For example by using an additional factor (New Covid Infections based on anti-Nucleocapside IgG between visits) in the MMRMs and performing analysis on the PP analysis set.

In further secondary analyses, it will be explored whether switching or keeping the same vaccine product for the 4th vaccination (study intervention in B) compared to the 3rd vaccination will have an effect. To evaluate such an impact models will be performed using for example the interaction between cohort and study drug or an indicator variable whether the 4th and 3rd vaccination are the same or not.

In addition to using the log10 scaled GMT values (=y) as dependent variable, we will use the relative change compared to the baseline value as dependent variable. The relative change is defined as $(Y_{\text{visit}} - Y_{\text{baseline}}) / Y_{\text{baseline}}$. The change might be presented as percentage change.

The secondary analyses will be performed overall and for cohorts separately.

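### SAP 9.7 and 9.3.2 base the reported infection proportions on the visit 2 anti-N result alone, which cannot give the day-14-to-month-12 proportion and does not separate baseline positives from new infections

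*SAP*

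**What the plan says.** SAP 9.7 begins with the sampling: "With testing for anti-Nucleocapside IgG at visits 1 (baseline), visit 2 (=d14) and visit 5 (end of study) subjects will be assessed for SARS-CoV-2 infection". It then undertakes to compare descriptively "the proportion of infections between d0, d14 and visit 5", and gives the basis in parentheses: "based on an anti-Nucleocapside IgG at visit 2 indicative of SARS-CoV-2 infection". Visits 1 and 5 are not named in that basis.

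SAP 9.3.2 opens with the same sampling statement and uses the same basis for the first interval: "the proportion of infections between d0 and d14 (based on an anti-Nucleocapside IgG at visit 2 indicative of SARS-CoV-2 infection".

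Other parts of the SAP use other bases:

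- The per-protocol sensitivity analysis in 9.3.2 keeps vaccinated participants "not having had a new infection between visit 1 and visit 2 using the anti-Nucleocapside IgG measurements of visit 1 and 2".
- The mixed-model factor in 9.4.3 is described as "New Covid Infections based on anti-Nucleocapside IgG between visits".
- The per-protocol set in 9.1 drops participants with a known new infection between baseline and the visit concerned.
- 9.3.2 adds a sensitivity analysis that excludes externally confirmed infections dated before the primary endpoint measurement.

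On eligibility, Protocol 4.4.2 excludes only recent infection: "Subject had COVID-19 or tested positive for SARS-CoV-2 within the last 3 months". Documented earlier infection is a randomisation stratum (Protocol 4.7.5) and a subgroup (Protocol 6.1.7, SAP 9.9).

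**The concern.** Two things go wrong if the parenthesis is applied as written.

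First, the sentence in 9.7 promises a result for the period after day 14 and then names a sample taken at day 14. The analyst cannot produce that result from the stated basis.

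Second, a positive visit 2 sample shows infection at some time before day 14. It does not show infection since randomisation. The eligibility rules admit people with older infections, so some may be positive before vaccination. Without the visit 1 result, those people and the newly infected fall into the same count.

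At stake is whether the reported infection proportions mean what their labels say. There is also a consistency problem. The proportions in 9.3.2 and the per-protocol analysis in the same section could classify the same participant differently. No section says what makes a result indicative of infection: there is no cut-off, no seroconversion rule and no fold rise. The trial is open-label (Protocol 4.7.8) and the SAP plans no blind data review (opening of section 9), so a rule chosen at analysis would be chosen with allocation visible.

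**Working it through.** The documents give no seroprevalence or infection rate, so there is no plan figure to reproduce. The main check is a comparison of the texts; the arithmetic afterwards is an illustration.

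**Step 1. Compare the bases.**

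| Place in SAP | Use | Basis stated | Suits its interval? |
|---|---|---|---|
| 9.3.2, proportions | Day 0-14, descriptive | Visit 2 | Only if nobody is positive at visit 1 |
| 9.7, proportions | Day 0, day 14, visit 5, descriptive | Visit 2 | Not for day 14 to visit 5 |
| 9.3.2, logistic factor | Infection between visits 1 and 2 | None stated | Criterion missing |
| 9.3.2, per-protocol sensitivity | New infection between visits 1 and 2 | Visits 1 and 2 | Yes, but no rule for baseline positives |
| 9.4.3, mixed-model factor | New infection between visits | Anti-N between visits | Yes, but no rule for baseline positives |
| 9.1, per-protocol set | Known new infection up to the visit | None stated | Criterion missing |

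The visit-2-only wording governs the first two rows. The parenthesis is the same in both, and in 9.7 it does not match the longer interval.

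**Step 2. Day 0-14 under a literal reading (assumed inputs).** Let p be the share anti-N positive at visit 1 and i the infection rate from day 0 to 14 among the rest. Assume baseline positives are still positive at visit 2 and that every new infection shows at visit 2.

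- Positive at visit 2: p + (1 - p)i
- Negative at visit 1 and positive at visit 2: (1 - p)i
- Share of counted cases already positive at baseline: p / [p + (1 - p)i]

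The planned Part B enrolment is 550 (Protocol 6.3). Assumed ranges are p = 5-30% and i = 1-5%.

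| p | i | Positive at visit 2 | Seroconverted | Already positive at baseline |
|---|---|---|---|---|
| 5% | 1% | 0.0595 x 550 = 33 | 0.0095 x 550 = 5 | 84% |
| 5% | 5% | 0.0975 x 550 = 54 | 0.0475 x 550 = 26 | 51% |
| 10% | 3% | 0.127 x 550 = 70 | 0.027 x 550 = 15 | 79% |
| 30% | 1% | 0.307 x 550 = 169 | 0.007 x 550 = 4 | 98% |
| 30% | 5% | 0.335 x 550 = 184 | 0.035 x 550 = 19 | 90% |

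Baseline positives outnumber seroconversions whenever p > (1 - p)i, that is p > i/(1 + i). For i = 5% the threshold is 0.05/1.05 = 4.8%; for i = 1% it is 0.01/1.01 = 1.0%. The shares do not depend on the 550.

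**Step 3. Day 14 to month 12 (assumed inputs).** With i = 3% and a later infection rate j of 10-50%, the number negative at visit 2 and positive at visit 5 is 550 x (1 - p)(0.97)j, assuming each such infection still shows at visit 5.

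- Lowest: p = 30%, j = 10% gives 550 x 0.70 x 0.97 x 0.10 = 37
- Highest: p = 5%, j = 50% gives 550 x 0.95 x 0.97 x 0.50 = 253

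A rule that looks only at visit 2 identifies none of these, whatever the rates.

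**The case against.** The strongest reply is that the parenthesis should be read with the sentence before it. Both 9.3.2 and 9.7 open by naming the baseline sample and visit 5 as part of assessing infection since randomisation, so the authors plainly meant to use them. On that view 9.7 contains a drafting slip. This is a fair account of intent, but it does not supply the missing rule. The only basis attached to the reported proportion is still visit 2, and no section says how a baseline-positive participant is classified.

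Several stronger readings are tempting, and the documents do not support them:

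- **That the SAP as a whole defines new infection from visit 2 alone.** The per-protocol sensitivity analysis works from paired results ("using the anti-Nucleocapside IgG measurements of visit 1 and 2"), and 9.4.3 works between visits.
- **That the plan counts previously infected people as new cases.** No section states this. It follows only from applying the parenthesis literally, and the real fault is an omitted criterion.
- **That infections after day 14 cannot be detected.** Anti-N is measured at visit 5, and dated external confirmations come in through adverse event reporting. The data exist; the stated basis does not use them.
- **That the regression models and the reading of month-12 titres rest on the visit 2 rule.** The logistic factor does not carry the parenthesis. For later titres, 9.4.3 plans an infection factor and a per-protocol analysis.

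The reply also notes, correctly, that the affected comparisons are descriptive and that every rate in the illustration is assumed.

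**Conclusion.** The point holds in a limited form. Two statements rest on the text alone: the basis given in 9.7 cannot produce the day-14-to-visit-5 proportion that its own sentence promises, and the basis given for day 0-14 in 9.3.2 does not, read literally, separate baseline positives from new infections. Both conflict with the paired and between-visit bases used elsewhere in the SAP.

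The direct effect is confined to the descriptive infection proportions in 9.3.2 and 9.7. The primary rate does not change, because SAP 9.1 keeps participants with a visit 2 result suggesting infection in the primary analysis population. The logistic, mixed-model and per-protocol uses are touched only in that they too lack a stated criterion.

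The size cannot be established from the documents. The 51-98% range depends on the literal reading, the assumed 5-30% baseline positivity and 1-5% 14-day incidence, and persistence of baseline positivity to visit 2. It shows that the distinction could dominate the count, not that it will. The correction should be made before analysis.

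**What to change.** In SAP 9.3.2 and 9.7, replace the visit 2 parenthesis with one paired rule for each interval: visit 1 to visit 2 for day 0-14, and visit 2 to visit 5 for day 14 to month 12.

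1. A new infection is anti-N negative at the start and positive at the end of the interval, or an externally confirmed infection dated within it.
2. For participants positive at the start, either apply a fold rise fixed from the assay's validation before analysis, or report them separately as not classifiable by serology. The SAP should say which.
3. State the assay cut-off for a positive result, and the denominator for each interval.
4. Use the same definition for the infection factors in 9.3.2 and 9.4.3 and for the per-protocol exclusions in 9.1 and 9.3.2.

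The cost is SAP wording, plus a cut-off (and a fold rise, if that option is chosen) from the laboratory. No visit, sample or assay is added, because anti-N is already scheduled at visits 1, 2 and 5.

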9.8 Multiplicity adjustment

The different pre-study vaccine combinations are considered as inferentially independent, as the prior vaccination strategy cannot be influenced and there will be no extrapolation from one cohort to another one for the primary analysis. Therefore, the multiplicity adjustment concerning the primary endpoint will be applied within each cohort, but there will be no further adjustment for having several cohorts within the accompanying master protocol. The comparison of treatment group is of secondary purposes, which are not subject of further multiplicity adjustments.

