2.2. Primary objective (Part B)

- To compare the immune response between treatment arms **after a 4th vaccination dose** against SARS-CoV-2.

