6.1.3. Primary analysis

All primary analyses will be on the mITT set. The primary endpoint is the rate π of 2-fold antibody titre increase following the 4th vaccine dose measured by quantitative enzyme-linked immunosorbent assay (Anti-RBD-ELISA) against wildtype virus at 14 days after the 4th vaccine dose (versus immediately before vaccination).

For the binary primary endpoint absolute and frequencies in percent will be calculated for each study part (Part A, Part B) and treatment group. For each study part and treatment group the corresponding rate together with simultaneous 95% confidence intervals will be calculated. Exact Clopper Pearson confidence intervals at Bonferroni adjusted level of $(1-0.05/2) * 100\%$ will be provided.

In additional supportive analysis, the primary endpoint will be performed in the same way for each cohort separately, i.e., further exploratory analyses will be performed based on different pre-vaccination series. Especially, within each cohort the multiplicity adjustment will be implemented.

The data will be visualised with bar charts.

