- To compare the immune response between treatment arms after a 4th vaccination dose against SARS-CoV-2.

Safety objective (Part B)

- To assess the safety of a 4th vaccination dose against SARS-CoV-2 in the study population.

Secondary objectives (Part B)

- To compare the humoral response against wild-type SARS-CoV-2 between treatment arms after a 4th vaccination dose against SARS-CoV-2.
- To evaluate descriptively the humoral response against SARS-CoV-2 variants of concern between treatment arms after a 4th vaccination dose against SARS-CoV-2.
- To evaluate descriptively the long-term humoral immune response of a 4th vaccination dose against SARS-CoV-2.

Exploratory objectives (Part B)

- To investigate the cellular immune response after a 4th vaccination dose, virus neutralizing capacity against newly emerging variants in bio-banked samples and correlates of interest.

2 General aspects of trial design

According to section 4.1 of the accompanying master protocol:

This is a randomised, adaptive, multicentre, Phase II master protocol evaluating different booster strategies in individuals against SARS-CoV-2. This protocol allows testing of different booster strategies to assess their immunogenicity and safety against SARS-CoV-2 and its variants. Different trial populations, different vaccines, additional doses and vaccination time points, and extended follow-up visits can be added throughout amendments of the master protocol. The master protocol contains a common control group that does not receive a 3rd nor a 4th vaccination, i.e., no booster dose at all. This control group is used for exploratory comparison as applicable. The trial implements a specific safety monitoring strategy for this control group.

2.1 Specific to this trial:

[figure not shown]

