9.3 Primary Endpoint Analysis

All primary analyses will be on the mITT set, consisting of all randomised subjects whose primary endpoint measurement is available. The primary endpoint is the rate π of 2-fold antibody titre increase following the 4th vaccine dose measured by quantitative enzyme-linked immunosorbent assay (Anti-RBD-ELISA) against wildtype virus at 14 days after the 4th vaccine dose (versus immediately before vaccination).

For the binary primary endpoint absolute and frequencies in percent will be calculated for each intervention group in Part B. For each treatment group in part B the corresponding rate together with simultaneous 95% confidence intervals will be calculated. Exact Clopper Pearson confidence

intervals at Bonferroni adjusted level of $(1-0.05/2) * 100\%$ will be provided (as there are two treatment groups in part B).

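### Part B's primary objective is to compare the two arms, but the primary analysis contains no comparison and no between-arm analysis is named as the answer

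*SAP*

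**What the plan says.** **Objective.** Protocol 2.2: "To compare the immune response between treatment arms". SAP 1 and both synopses say the same for Part B.

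**Primary analysis.** SAP 9.3: "For each treatment group in part B the corresponding rate together with simultaneous 95% confidence intervals will be calculated". Protocol 6.1.3 gives the method: "Exact Clopper Pearson confidence intervals at Bonferroni adjusted level of" 1 − 0.05/2, that is, 97.5% per arm. Neither section contains a difference, ratio, hypothesis or margin.

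**Between-arm analyses and their rank.**
- SAP 9.3.1, headed as supportive, has a CMH test stratified by cohort, with this purpose: "To evaluate whether there is a difference between the two randomised intervention groups in the binary primary endpoint". It also has a logistic odds ratio, where "we will also adjust for factors such as initial vaccination regimens (factor cohort), age and sex". Protocol section 6 has neither.
- Protocol 6.1.4 and SAP 9.4.2 have a day-14 GMT equivalence test (margins 0.67 to 1.5, or ±0.174 on the log10 scale), called secondary. Its model includes all randomisation strata.
- SAP 9.8 covers every comparison: "The comparison of treatment group is of secondary purposes, which are not subject of further multiplicity adjustments".

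**Sample size.** Protocol 6.3 and SAP 12.1 size the trial on per-arm precision: 250 evaluable per arm, at most ±7.1 points. SAP 12.1 adds that 550 subjects give enough power to compare GMTs, without an SD, a true ratio or a power figure.

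**Dose intervals.** SAP 9.3.1: "We will also account for the different time lags between the 2nd and 3rd doses in further sensitivity analysis". SAP 9.4.3 names the 3rd-to-4th-dose interval as well.

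**The concern.** The primary objective asks a comparative question and the primary analysis does not answer it. The analyses that could answer it are all ranked below primary. A report that follows the plan exactly would give two rates as its primary result and then have to decide, with results in hand, whether and how they answer the stated objective. The trial is open-label (Protocol 4.7.8) and SAP 9 foresees no blind data review, so a decision left until then could not be shown to be independent of the data. If per-arm estimation is what was meant, the objective sentence promises something else.

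**Working it through.** **1. The plan's own figure.** Inputs from SAP 12.1: n = 250 per arm, rate 50%, two-sided 0.05/2 = 0.025, so z = 2.2414.

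Half-width = z·√(0.25/n) = 2.2414 × √(0.25/250) = 0.0709, stated as 0.071. The rest of the table reproduces: 0.0792, 0.0915, 0.1002, 0.1181, 0.1585 and 0.1772 for n = 200, 150, 125, 90, 50 and 40. For total N, 500/(1 − 0.09) = 549.5, in line with 550. The trial is therefore sized for two single-arm estimates.

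**2. Can the two intervals serve as the comparison?** The Bonferroni factor protects joint coverage of two rates. Declaring a difference only when two 97.5% intervals do not overlap is a two-sided test at 2·[1 − Φ(2 × 2.2414/√2)] = 0.0015 (equal n and rates, normal approximation). That is not a planned contrast at 0.05.

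**3. Precision of a contrast on the primary endpoint.** With 250 per arm and both arms at rate p, the half-width is 1.96·√(2p(1 − p)/250).

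| p (assumed) | 95% half-width, points |
|---|---|
| 50% | 8.8 |
| 70% | 8.0 |
| 90% | 5.3 |

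**4. Prior COVID-19 in the logistic model.** It is a randomisation stratum (Protocol 4.7.5, SAP 6) that SAP 9.3.1 does not name. At a marginal rate of 50%, adjustment multiplies the variance by 1 − q(1 − q)g²/0.25, where q is the share previously infected and g the gap in response. With q = 10% and g = 20 points the factor is 0.986 and the half-width 8.7. With q = 30% and g = 40 points it is 0.866 and 8.2. Both q and g are assumptions; the gain is modest.

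**5. The GMT power claim.** SE = SD·√(2/250). The critical value is c = 1.965 (t, 491 df: 500 subjects less 9 parameters for intercept, vaccine, five cohort terms, sex and prior infection). With d = log10(true ratio), power = Φ((0.174 − d)/SE − c) − Φ(−(0.174 + d)/SE + c). The documents give no SD, so a range is shown.

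| log10 SD (assumed) | true ratio 1.0 | true ratio 1.2 |
|---|---|---|
| 0.4 | 99.6% | 75.3% |
| 0.5 | 94.6% | 56.2% |
| 0.6 | 79.9% | 41.9% |
| 0.7 | 58.5% | 30.7% |

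Power of 80% needs an SD of at most about 0.60 at ratio 1.0, or 0.38 at ratio 1.2.

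**6. Precision of the interval that will be reported.** The stated figures use the normal approximation. Exact 97.5% Clopper-Pearson limits at 125/250 are 42.76% and 57.24%.

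| n | stated | exact, at 50% | exact, largest distance to a limit |
|---|---|---|---|
| 250 | 7.1 | 7.2 | 7.3 |
| 40 | 17.7 | 18.2 | 18.9 |

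**The case against.** The best defence is that this is a coherent Phase II estimation trial. Both synopses rank per-group rates first, the vaccine comparison second and homologous versus heterologous boosting third. Protocol 4.2 and SAP 3 justify the sample size by precision of estimation, and SAP 9.8 says openly that comparisons are secondary. This carries weight: it makes rewording the objective at least as natural as promoting a contrast. It does not remove the mismatch, because the objective sentence still promises a comparison.

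One could also say that the CMH test is the implied answer, since its stated purpose is a difference in the primary endpoint. But it sits under a supportive heading, SAP 9.8 ranks it as secondary, and Protocol section 6 does not contain it.

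Three stronger readings are tempting, and the documents do not support them:
- A reader might infer that the CMH p-value, the odds ratio and the GMT ratio are three rival answers, open to free choice. The first two share one endpoint. The GMT is a different variable, labelled secondary, and fits its own secondary objective of comparing humoral response to wild-type virus. These labels limit selection after the fact, though they do not designate an answer.
- A reader might infer that the interim rule in SAP 9.10, which controls the family-wise error for the primary endpoint, has nothing to control. Simultaneous intervals have a family-wise non-coverage rate, and the same section applies its boundary to the primary-analysis intervals. The wording has a referent.
- A reader might infer that small cohorts will break the logistic model, so that a rule for merging cohorts and a fallback estimator are needed. In simulation (500 subjects, assumed cohort shares 60/20/5/5/8/2%, log odds ratio 0.3, 90% reference response) a cohort was fully separated in about 38% of trials, yet coverage of the treatment odds ratio stayed near 95%. Separation affects only that cohort's nuisance coefficient.

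**Conclusion.** The point holds as a mismatch between objective and analysis. It is not an arithmetic error and does not show that the trial is too small. It should be fixed before the primary analysis, because the plan as written does not answer its own primary question.

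The risk-difference half-widths rest on 250 evaluable per arm and equal rates in the arms. The GMT power figures also rest on assumed SDs and true ratios, so the finding there is that the claim is unsupported, not that it is false. The exact-interval figures need no assumption beyond n; they exceed the stated maximum by 0.1 to 0.2 points at n = 250 and by 0.5 to 1.2 points at n = 40. The missing stratum and the missing dose interval are minor: the logistic model is valid without prior COVID-19, only somewhat less efficient.

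**What to change.** (a) Make objective and analysis agree in Protocol 2.2 and 6.1.3 and SAP 1, 9.3 and 9.8, and carry the wording into both synopses. Choose one:
- (i) Reword the primary objective as estimation of the 2-fold response rate in each arm, with comparisons secondary, as SAP 9.8 already has it.
- (ii) Keep the objective and designate one contrast on the primary endpoint: the risk difference, mRNA-1273 minus BNT162b2, with a two-sided 95% interval and its expected precision. Keep the per-arm intervals, and keep GMT equivalence as secondary.

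(b) In SAP 9.3.1, put all randomisation strata (vaccine series, sex, prior COVID-19 yes/no) in the logistic model, as SAP 9.4.2 does for GMT.

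(c) In SAP 12.1, give the SD and true ratio behind the GMT power claim, or delete the claim.

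(d) Restate per-arm precision for the Clopper-Pearson interval, in Protocol 6.3 as well as SAP 12.1.

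(e) Minor: add the 3rd-to-4th-dose interval to the SAP 9.3.1 sensitivity analysis, as in SAP 9.4.3.

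Cost: no new subjects, visits or assays, and N stays at 550. Items (b), (c) and (e) are SAP edits. Items (a) and (d) also touch the protocol; a change judged significant needs authority approval and a favourable ethics opinion (Protocol 9). SAP 9.2 describes subjects as already randomised and the trial is open-label, so option (ii) should be dated and fixed before any between-arm result is seen, including any from the interim look.
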